7.3.1. Assessment of AEs and SAEs

7.3.1.1 Severity

The Investigator will determine the severity of the AE;

- Mild: no interference with daily activities.
- Moderate: moderate interference with daily activities.
- Severe: considerable interference with daily activities (e.g. inability to work).

NOTE: to avoid confusion or misunderstanding the term "severe" is used to describe the intensity of the event, which may be of relatively minor medical significance, and is NOT the same as "serious" which is described in the safety definitions.

7.3.1.2 Causality

Clinical judgement will be used to determine the relationship between the study procedures and the occurrence of each AE;

- Not-related: There is no evidence of a causal relationship between the event and study procedures.
- Related: There is evidence of a causal relationship between the event and study procedures, i.e., a relationship to the study procedures cannot be completely ruled out.

Assessment of causality must be made by a medically qualified doctor (usually the Principal Investigator).

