7.2. Operational Definitions for (S)AEs

An adverse event (AE) in this pilot trial is any untoward medical occurrence in a participant to whom a trial intervention or procedure has been delivered, including occurrences which are not necessarily caused by or related to that intervention or procedure.

Examples of AEs which may be expected would be:

- Re-ulceration
- New ulcer
- Ulcer infection

AEs which are NOT considered related to the intervention or procedure do not need to be reported unless they are considered SAEs.

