7.3. Recording and Reporting SAEs

HCPs will record all directly observed AEs and all SAEs reported by the trial participants up to the final follow-up assessment. In addition, sites should follow their own local procedures for the reporting of any adverse events linked to clinical care.

Adverse events should be entered onto the Adverse Event reporting form and reported to York Trials Unit within five days of discovery or notification of the event.

SAEs should be entered onto the Serious Adverse Event reporting form and reported to York Trials Unit within 24 hours of discovery or notification of the event. Once received, causality and expectedness of the SAE will be confirmed by the Chief Investigator or another clinical member of the Trial Management Group (if the CI is unavailable).

SAEs that are deemed to be unexpected and related to the trial will be notified to the Research Ethics Committee (REC) and Sponsor within 15 days. All such events will be reported to the Trial Steering Committee at their next meeting.

All events will be followed up until the event resolves or a decision is made for no further follow up. Participants experiencing SAEs which are deemed to be related to the trial treatments (intervention or control) and which remain ongoing at the time of participant trial exit will be followed up for one further month beyond trial exit.

Where repeated adverse events (serious or non-serious) of a similar type are observed, these will be discussed with the TMG and other relevant groups and will be onward reported to the REC and Sponsor should concerns be raised in relation to the type of event and/or frequency observed.

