7.3.1.3 Expectedness

The assessment of expectedness is only required if the event is deemed to be related to study procedures.

- Expected: Event previously identified and described in the protocol.
- Unexpected: Event not previously described in the protocol.

The expectedness assessment is delegated to the local PI.

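### The two causality categories in section 7.3.1.2 overlap: an event with no evidence of causation that cannot be ruled out is both related and not related

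*Protocol*

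**What the plan says.** Protocol section 7.3.1.2 uses a two-category causality scale based on clinical judgement. The not-related category reads: "There is no evidence of a causal relationship between the event and study procedures". The related category requires "evidence of a causal relationship between the event and study procedures, i.e., a relationship to the study procedures cannot be completely ruled out".

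Several rules depend on that label:

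- **Non-serious events (7.2):** "AEs which are NOT considered related to the intervention or procedure do not need to be reported unless they are considered SAEs".
- **Expectedness (7.3.1.3):** "The assessment of expectedness is only required if the event is deemed to be related to study procedures".
- **Serious events (7.3):** "SAEs that are deemed to be unexpected and related to the trial will be notified to the Research Ethics Committee (REC) and Sponsor". The time limit for this is 15 days. The Trial Steering Committee hears of these events at its next meeting. Serious events related to trial treatment and still ongoing at trial exit are followed for one further month.

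On who decides, 7.3.1.2 asks for a medically qualified doctor, usually the local principal investigator, to judge causality. Section 7.3.1.3 states: "The expectedness assessment is delegated to the local PI". Section 7.3 adds that, once the form for a serious event has been received, "causality and expectedness of the SAE will be confirmed by the Chief Investigator or another clinical member of the Trial Management Group", the second of these acting if the Chief Investigator is unavailable.

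**The concern.** A two-category scale works only if every event falls into exactly one category. Here the related category is stated as a positive finding (there is evidence) and then explained by a much weaker test (causation has not been excluded). The not-related category is the complement of the first test but not of the second.

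The gap between the two tests is where many events in this trial could sit. REDUCE works on physical activity, foot checking and self-referral (section 1.1), and a link between such coaching and a later foot problem may be hard either to show or to exclude. Two assessors following the same text could label such an event differently. The difference would pass into the non-serious events reported, into who is told about a serious event, and into the descriptive adverse event summary by group (section 9.4). The pilot has no Data Monitoring and Ethics Committee, and its data may be carried into the main trial (sections 1.3 and 6.9), so a consistent label has some value beyond the pilot.

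**Working it through.** No arithmetic applies. The check lists the possible states of an event and applies each wording.

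**Step 1: states.** There are two yes/no questions: is there evidence of causation, and can a relationship be completely ruled out? Evidence together with exclusion is incoherent, which leaves three states.

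| State | Evidence | Ruled out | Meets not-related wording | Meets related, evidence wording | Meets related, explanatory clause |
|---|---|---|---|---|---|
| 1 | yes | no | no | yes | yes |
| 2 | no | yes | yes | no | no |
| 3 | no | no | **yes** | no | **yes** |

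States 1 and 2 have one label each. State 3 satisfies the not-related definition and the explanatory clause of the related definition, so the text gives it no unique label.

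**Step 2: what the label changes for a state 3 event.**

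| Decision | If labelled related | If labelled not related |
|---|---|---|
| Non-serious event reported (7.2) | yes | not required |
| Expectedness assessed (7.3.1.3) | yes | not required |
| Serious event can qualify for 15-day notification and steering committee reporting (7.3) | yes, if also unexpected | no |
| Serious event ongoing at exit followed one further month (7.3) | yes, if related to trial treatment | no |

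**Step 3: what the label does not change.** All serious events go to York Trials Unit within 24 hours (7.3). The three-month notes review by blinded assessors collects re-ulceration, number of ulcers, amputations, hospital days, deaths and adverse events, with no causality condition (6.6.1). The stop-go criteria (9.2) concern recruitment and data collection, not adverse events.

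**Step 4: related to what?** The object of the relationship varies across section 7:

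- 7.1: the study ulcer and/or the study treatments, including control, as part of the definition of an adverse event;
- 7.2: the intervention or procedure;
- 7.3: the trial, for notification, and the trial treatments including control, for follow-up after exit;
- 7.3.1.2 and 7.3.1.3: study procedures.

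Control participants receive usual care only (6.3). An event linked to usual care could count as related where control treatment is named, and arguably not where only study procedures are.

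**Step 5: who decides.** Sections 7.3.1.2 and 7.3.1.3 give the assessment to the site; 7.3 gives confirmation for serious events to the centre. The two steps are compatible. What is not stated is whose view stands if they differ.

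**The case against.** The best defence of the text is that the clause after 'i.e.' explains the one before it, so the working test is the inclusive one. A reader who follows it would put state 3 under related. That is a fair reading, but the separate not-related definition still claims the same event, so the overlap remains.

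It can also be said that central confirmation of serious events brings sites into line. It may do so for serious events. Non-serious events have no such step, and the confirmer works from the same definitions.

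Four stronger readings are tempting, and the documents do not support them:

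- **That 7.3 and 7.3.1.3 contradict each other on expectedness.** One speaks of assessment by the local investigator, the other of confirmation after receipt. That reads naturally as two stages. Nothing says the confirmer may downgrade a site's judgement; the text is silent on disagreement, and a form or procedure not shown here may cover it.
- **That re-ulceration could be missed for expedited reporting because of the overlap.** Section 7.2 lists re-ulceration, new ulcer and ulcer infection as examples of events that may be expected, and 15-day notification needs an unexpected event. For these three, the causality label affects non-serious reporting, not the 15-day route.
- **That the related share could swing between almost none and almost all.** The protocol gives no event rate and no proportion of events in state 3, so no range can be derived.
- **That every difference in reference wording is an error.** The follow-up rule in 7.3 may be intentionally narrower. The variation needs to be reconciled or explained; the text does not show which phrase is intended.

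**Conclusion.** The causality categories overlap, and the label governs real reporting decisions. Related-event counts, non-serious reports and, for events not listed as expected, notifications could differ between assessors applying the same text.

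The consequence is limited. Serious events and ulcer outcomes are captured whatever the label. Adverse events are only summarised descriptively, in a pilot of 15 to 20 participants, and no estimate or progression criterion depends on the label. No numerical size can be given. The point is a wording defect that should be corrected, not a threat to the trial's conclusions.

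This rests on two assumptions: that some events will fall in state 3, which is plausible for a behavioural intervention but not quantified in the protocol, and that no form or procedure outside the protocol already resolves the overlap. The missing rule for disagreement between local assessor and central confirmer is a minor addition.

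**What to change.** 1. In 7.3.1.2, use one threshold and make not related its exact complement. One way that stays close to the present text is to keep the test that a relationship cannot be completely ruled out and to define not related as a relationship that can be ruled out. A higher threshold, such as a reasonable possibility of causation, would also give exclusive categories, but it raises the bar relative to the present explanatory clause and would tend to reduce related reports. Choosing it should be deliberate.
2. Reconcile the object of the relationship in 7.1, 7.2, 7.3, 7.3.1.2 and 7.3.1.3. Say whether usual care in the control arm counts, and if the follow-up rule is meant to be narrower, say so.
3. As a minor addition to 7.3, state whose view of causality and expectedness stands when the local assessor and the central confirmer differ.

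The cost is a few lines in the protocol and matching wording on the event forms. Keeping the inclusive threshold may bring a few more adverse event forms and some extra expectedness assessments.

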7.3.1.3 Expectedness

The assessment of expectedness is only required if the event is deemed to be related to study procedures.

- Expected: Event previously identified and described in the protocol.
- Unexpected: Event not previously described in the protocol.

The expectedness assessment is delegated to the local PI.

7.4. Pregnancy Reporting

Not required.

7.5. Reporting Urgent Safety Measures

If any urgent safety measure is required the research team should inform the Sponsor within 24 hours. The participating site will notify York Trials Unit within 24 hours. York Trials Unit will notify the Sponsor using the Sponsor's safety incident reporting form. Any immediate actions will be advised to the research teams at sites in writing. Study teams will be asked to confirm receipt and implementation of any action.

The Sponsor will inform the REC and in conjunction with YTU and the Chief Investigator will advise participating sites. This will be followed up within three days by notice in writing setting out the measures taken and the circumstances giving rise to those measures within three days on implementation of the urgent safety measure, with a plan for further action.

8. DATA HANDLING

A separate Data Management Plan (DMP) will be in place for the handling of the data between participating NHS sites, York Trials Unit and the research team.

8.1. Data Collection Tools and Source Document Identification

Data collected as part of this research includes questionnaires, clinical assessments, web-usage data and interview audio recordings. Data will be collected through designed questionnaires paper CRFs.

Baselines clinical assessment CRFs will be completed on paper at the participating NHS Trust/site and the data will be managed by York Trials Unit. A copy will be retained for the trial site file. Follow-up clinical assessment will be completed in a paper format by the outcome assessors at the research site and the data will be managed by YTU.

The participant completed CRFs (baseline, 6 week and 3 month follow-up) and home practice questionnaires, will be received and entered by the University of Nottingham research team and returned to York Trials Unit at regular intervals.

Web-usage data is collected via Matomo Analytics. Information regarding data security is available here: https://matomo.org/gdpr-analytics/ [accessed 25 January 2021]. This data will be provided to York Trials Unit for the final dataset, and will be accessed by research teams at the University of Nottingham, King's College London, University of Edinburgh and Swansea University.

8.2. Source Data

Source documents are original documents, data, and records from which participants' study-specific data are obtained. These include, but are not limited to, medical records (from which medical history and previous and concurrent medication may be summarised into the study-specific documentation, clinical observation records, diaries, correspondence, completed scales, quality of life questionnaires, interview audio recordings, interview transcripts and web-usage data). Study documentation entries will be considered source data if the form is the site of the original recording (e.g., there is no other written or electronic record of data). In this study, the study documentation will be used as the source document as outlined in the Source Data Verification form.

All documents will be stored safely in confidential conditions. Any paper forms containing participant identifiable information (e.g. participant details form and consent form) will be held in a location separate to the questionnaire data. Outside of the NHS Trust, Identifiable information will be stored securely in a locked filing cabinet, in an office only accessible via registered swipe card access held by the York Trials Unit research team (As per YTU Standard Operating Procedure YT03).

Personal data held electronically, will be stored on the study specific participant management system which will record identifiable information and participant activity to enable study coordination. This will be accessible via individual password. Permissions for access of this information will also be detailed within the trial delegation of responsibilities log. The server on which the management system will be housed is secure and is subject to rigorous testing and continued backup.

The original copy of the participant consent forms will be stored at the participating NHS Trust. A copy will also be sent securely electronically to York Trials Unit for storage in the Trial Master File

 $REDUCE\ Pilot_Protocol_v1.1_25 May 2021.$

and to enable centralised monitoring. A copy will also be sent (securely) to University of Nottingham to verify consent for the questionnaires and, for the intervention arm, to arrange intervention sessions and provide intervention materials, to University of Edinburgh to verify consent to interview and to Kings College London for audio recording of intervention delivery.

8.3. Data Handling and Record Keeping

Each site will hold data according to the current Data Protection Act (2018) and the General Data Protection Regulation (2018). Data will be collated in CRFs identified by a unique identification number (i.e. the participant identification number) only. A Trial Enrolment Log held at individual sites will list the participant identification numbers. YTU will maintain a list of participant identification numbers for all trial participants at each site.

All information collected during the course of the study will be kept strictly confidential. Personal addresses, postcodes and other contact details of consenting participants will be stored on the study specific participant management system at YTU, for the purposes of assisting in follow ups during the study. Only relevant members of the research team will have access to this system, accessible via individual password. Permissions for access of this information will be detailed within the study delegation log. All participant data will be coded by a participant number in all manual and electronic files to ensure confidentiality.

Data from the paper forms will then be manually entered into a database which will be second checked against the hard copy of the questionnaire. Data is error checked and then validation checks are run against the database. Discrepancies identified during validation which require resolution will be communicated to the relevant person who is in a position to obtain the information required to rectify the discrepancy.

Information will be held securely on paper and electronically at the above mentioned departments, including appropriate storage, restricted access and disposal arrangements of participant personal and clinical details. Participants will not be identified in the results of the study. Personal data will be processed under Article 6 (1) (e) (Processing necessary for the performance of a task carried out in the public interest) and Special Category data under Article 9 (2) (j) (Processing necessary for ... scientific ... research purposes) of the General Data Protection Regulation (2018).

Anonymised copies of the data (e.g. questionnaires, intervention session recordings, fidelity tool data, training and attendance records) will be retained for a period of five years and thereafter destroyed. Data with personal information (including contact details forms and audio recordings) will be deleted after the study period and write-up are complete (maximum three years after study end). Personal data considered source data, e.g. names on consent forms and in the enrolment log will be retained for five years.

8.3.1. Pilot Trial Participant Data

Anonymised case report form data will be stored in a database held at the University of York. This data is only accessible by relevant members of the data management team who are responsible for checking and validating the data. This will be accessible via individual password. Permissions for access of this information will also be detailed within the study delegation log. The server on which

the database will be housed is secure and is subject to rigorous testing and continued backup. Once finalised and locked, the dataset will be transferred to those responsible for the analyses.

The REDUCE Pilot Trial Management system will be used to record participant details, and CRF completion. This will be accessible via individual password to those listed on the study delegation log. The server on which the management system will be housed is secure and is subject to rigorous testing and continued backup. Once finalised and locked, the dataset will be transferred to those responsible for the analyses.

All documents will be stored safely in confidential conditions. Any paper forms containing participant identifiable information (e.g. patient contact details form and consent form) will be held in a location separate to the questionnaire data. Identifiable information will be stored securely in a locked filing cabinet, in an office only accessible via registered swipe card access held by the York Trials Unit research team (As per YTU Standard Operating Procedure YTO3).

8.3.2. Health Economic Data

For the health economic analysis, unit cost information will be collected or estimated to ensure these costs are available or can be generated (e.g. from local financial records or literature) prior to the main trial.

8.3.3. Nested Qualitative Study Data

All interview recordings and transcripts will be given a unique participant identifier.

The interviews will be audio-digitally recorded on an encrypted audio recorder and stored as digital files and transcribed into Word files. All identifying features (e.g., names, places) will be removed during the transcription process. There will be no identifying information (names, etc.) used to denote these digital files.

The audio-digital files will be transcribed by a professional transcription agency. The researcher of UoE will use the DataSync cloud service (or equivalent) operated and hosted by the University of Edinburgh (see: https://www.ed.ac.uk/information-services/computing/desktop-personal/datasync [Accessed 4 March 2020]. Files on DataSync are only visible to other people if they are shared. Digital audio recordings of interviews will be uploaded to DataSync and an encrypted and time-limited link sent to a professional transcription company to enable the file to be downloaded. Transcripts of audio files will be returned to the researcher using password-encrypted Word files. The transcription company will be asked to sign a confidentiality agreement, including a section which acknowledges that any recordings downloaded or transcript files will be deleted after being sent to the researcher. Following transcription, only the research team will have access to the raw data or transcripts.

Data will be stored on the University of Edinburgh network, accessible by user id and password. Data will be password protected. At no point will digital or paper files of the final transcript contain any identifying information. Files containing contact details will be encrypted and password-protected.

8.3.4. Fidelity Assessment Data

Intervention session audio recordings will be obtained by the healthcare professional delivering the REDUCE intervention via an encrypted digital audio recorder or via an NHS approved system, e.g.

Microsoft Teams. Recordings will be uploaded and stored initially on NHS computers. Healthcare professionals will transfer the audio files to the King's College London research team via email from their nhs.net email addresses using NHS encryption.

Intervention session audio recordings and fidelity assessment tool data will be given identifiers to ensure confidentiality. Data will be stored on Kings College London servers, backed up and accessible only by members of the research team on the delegation log who have university usernames and passwords.

